4.5.2 Main analytical approach

The correlation between TIR and participant-reported outcomes (PRO) and TIR and HbA1c at week 16 will be assessed using Pearson’s correlation coefficient. A contingency table will be constructed based on TIR > 70% and participants requiring 60 units/day of insulin glargine at week 16. If all the expected cell counts exceed 5, the association will be tested by chi-square test; otherwise, Fisher’s exact test will be used.

Mean (SD) and associated 95% CI, as well as minimum, median, and maximum values will be provided for continuous variables for change from baseline. The correlation endpoint tables present “n” being number of participants (xx) and correlation coefficient value (0.xxx). For correlation between change in TIR and PRO, a table will present PRO data for overall scores and subscale/domain scores and a 95% CI. Participants with non-compliant or missing data at week 16 will be excluded from the analysis.

For change in diabetes medication treatment-related impact and satisfaction, as measured by the DM-SAT, at baseline (run-in) and week 16, the mean (SD) and associated 95% CI, as well as minimum, median, and maximum values will be presented for overall score and by subscales/domains. The 16-item questionnaire is measured from 0-10: 0 = Not at all satisfied, 1-3 = Not too satisfied, 4-6 = Somewhat satisfied, 7-9 = Very satisfied, 10 = Extremely satisfied. The score for each the 4 domains/subscales is calculated as follows: lifestyle (sumscore lifestyle of 5 questions)/50; medical control (sumscore medical control of 3 questions)/30; convenience (sumscore convenience of 5 questions)/50 and well-being (well-being sumscore of 3)/30. The overall score will be calculated by: (sumscore overall of 16 questions)/160. If there are more than 25% missing items for a scale, the scale will be treated as missing. For the greatest measurement precision, it is recommended to use the full 16-item DM-SAT total score to assess overall treatment satisfaction in research applications, as a study outcome. There will be no reverse scoring as it is not applicable to the DM-SAT items.

A summary descriptive analysis of TIR, TAR, and TBR will be provided with no imputation for missing data. This will be provided under the Descriptive Analyses tables.

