4.5 TERTIARY/EXPLORATORY ENDPOINT(S) ANALYSIS

4.5.1 Definition of endpoint(s)

Mean changes for continuous outcomes for additional measures of glycemic control and variability in participants with T2DM:

- Change (mg/dL) from baseline (run-in) to week 16 in mean of daily difference [MODD] of glucose levels. Using the formula: $\frac{\sum_{t=0}^{t=95} |[Day_{j+1,t} - Day_{j,t}]|}{\text{number of paired timepoints}}$ where t =time period in the 24 hour day by 15 minute intervals and j = day to calculate MODD for each participant 13 times comparing Day 2 to Day 1, up to Day 14 to Day 13 for Baseline and for week 16. The average absolute daily differences at each 15-minute interval of CGM data will be summarized using descriptive statistics. Two-sided 95% CI will be presented.
- Change (%) from baseline (run-in) to week 16 in TAR >250 mg/dL. The percentage of time spent above the glycemic target range will be calculated as 100 times the number of the total number of 15-minute increments of CGM data where a participant’s blood glucose falls above normal range (>250 mg/dL) in a 14-day period divided by the total number of 15-minute increments read (1344 number of 15-minute increments). This will

be calculated for baseline and for week 16 to report the difference. A two-sided 95% CI will be presented.

- Change (%) from baseline (run-in) to week 16 in TBR <70 mg/dL. The percentage of time spent below the glycemic target range will be calculated as 100 times the number of the total number of 15-minute increments from CGM data where a participant's blood glucose falls below normal range (<70 mg/dL) in a 14-day period divided by the total number of 15-minute increments read (1344 number of 15-minute increments). This will be calculated for baseline and for week 16 to report the difference. A two-sided 95% CI will be presented.
- Correlation of change in percentage of TIR [70 – 180 mg/dL] and change in PRO from baseline (run-in) to week 16. Analysis will be done between each of the 4 domains (well-being, medical control, lifestyle, and convenience), PRO overall, and change in TIR. The purpose of finding the correlation of change from baseline to week 16 for percentage of TIR and PRO is to determine the relationship between those two continuous variables.

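### Applied as written, the DM-SAT formulas score a skipped item in a retained scale as the worst answer, because the denominator stays at the full-scale maximum

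*SAP*

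**What the plan says.** SAP 4.5.2 sets the item range and anchors the bottom of it: "The 16-item questionnaire is measured from 0-10: 0 = Not at all satisfied". It then gives one formula per scale, each a sum over a constant:

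- "lifestyle (sumscore lifestyle of 5 questions)/50"
- "convenience (sumscore convenience of 5 questions)/50"
- "medical control (sumscore medical control of 3 questions)/30"
- "well-being (well-being sumscore of 3)/30"
- the overall score, followed directly by the only rule on missing items: "sumscore overall of 16 questions)/160. If there are more than 25% missing items for a scale, the scale will be treated as missing"

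The item counts agree with Protocol 6.2.6 (3, 3, 5 and 5, total 16). SAP 4.5.1 bases the DM-SAT change on enrolled participants whose outcomes are available at both visits. SAP 5.4.4 (missing data) and Protocol 8.7.7 (PRO analysis) do not address gaps at item level. Neither document contains proration, item imputation or an adjusted denominator.

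The scores are used twice: as the PRO endpoint (total and subscales) and in an exploratory analysis, "Correlation of change in percentage of TIR [70 – 180 mg/dL] and change in PRO from baseline (run-in) to week 16", which is run for each domain and for the overall score.

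**The concern.** The retention rule deliberately admits incomplete scales, but the formulas fit only complete ones. Where the two meet, the written arithmetic treats no answer as complete dissatisfaction.

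A gap at one visit only then creates a change in satisfaction that did not occur. At Week 16 it looks like worsening. At baseline it looks like improvement, which is the direction SAP 4.5.1 expects. The trial has one arm, so no comparator can offset the artefact. The overall score, which SAP 4.5.2 recommends for assessing overall satisfaction, can carry the most gaps. Each distorted change also enters the TIR correlations as an individual data point.

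**Working it through.** **Inputs.** Item range 0 to 10, items per scale, denominators and the 25% rule, all from SAP 4.5.2. The documents give no item skip rates and no expected DM-SAT means, so those used in step 4 are assumptions.

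**1. Reproduce the denominators and apply the retention rule.** The denominator should be 10k for k items. A scale with m gaps is kept when m/k is at most 25%.

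| Scale | k | 10k | SAP denominator | Most gaps kept |
|---|---|---|---|---|
| Lifestyle | 5 | 50 | 50 | 1 (20%) |
| Convenience | 5 | 50 | 50 | 1 (20%) |
| Medical control | 3 | 30 | 30 | 0 (1 of 3 = 33.3%) |
| Well-being | 3 | 30 | 30 | 0 (1 of 3 = 33.3%) |
| Overall | 16 | 160 | 160 | 4 (25.0%; 5 of 16 = 31.25%) |

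All five denominators are right for complete scales. The 3-item subscales become missing at one gap, so they are never scored wrongly themselves. That same gap still enters the overall sum as 0.

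**2. Size for one participant.** Let S be the sum of the answered items.

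- As written: S/(10k).
- Over answered items only: S/(10(k − m)).
- Ratio: (k − m)/k = 1 − m/k.

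If the skipped items would have matched the answered ones, the relative loss is m/k: 20% for 1 of 5, and 6.25%, 12.5%, 18.75% or 25% for 1, 2, 3 or 4 of 16. For someone answering 7 throughout, whose score should be 0.70:

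- 1 of 5 skipped: 28/50 = 0.56 (−0.14).
- 1 to 4 of 16 skipped: 105/160 = 0.656, 98/160 = 0.613, 91/160 = 0.569, 84/160 = 0.525 (−0.175 at four).

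**3. Effect on that participant's change.** Suppose the answers move from 5 to 7, a true change of +0.20. With one lifestyle item skipped at Week 16 only, the recorded change is 0.56 − 0.50 = +0.06. Skipped at baseline only, it is 0.70 − 20/50 = +0.30.

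**4. Effect on mean change.** Assume item means of 5 at baseline and 7 at Week 16 (true change +0.200), with skipping unrelated to satisfaction. Let r_b and r_w be the proportions of participants skipping at each visit, and f the fraction of items skipped. Then mean change = 0.7(1 − f·r_w) − 0.5(1 − f·r_b).

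| r_b | r_w | 1 of 5 (f = 0.20) | 4 of 16 (f = 0.25) |
|---|---|---|---|
| 0 | 5% | +0.193 | +0.191 |
| 0 | 10% | +0.186 | +0.183 |
| 0 | 20% | +0.172 | +0.165 |
| 10% | 0 | +0.210 | +0.213 |
| 10% | 10% | +0.196 | +0.195 |
| 20% | 20% | +0.192 | +0.190 |

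The 4-of-16 column is an upper case: every participant who skips is taken to skip the maximum number kept.

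**The case against.** The strongest reply is that the SAP never says a skipped item counts as 0. Its formulas describe a full set of answers, and the sum of 16 questions is undefined when only 12 are answered. The sponsor may intend proration. This stands as a limit on wording: zero scoring is the arithmetic result of the formula, not a stated rule. It does not remove the problem. The only written formula gives the wrong score for a scale the SAP chooses to keep, and a program that returned missing for any incomplete sum would leave the 25% rule with nothing to do.

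Other points stand in part:

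- A reader might infer that every skipped item is scored as the worst answer. That holds only for scales kept under the 25% rule.
- The four-gap case assumes the rule for a scale also covers the overall score. That is the natural reading, but SAP 4.5.2 does not say so.
- A reader might infer a known bias in the PRO result. The documents give no skip rate and do not describe how the form is captured. Both administrations are clinic visits under the same instructions, so similar skipping at each is plausible, and step 4 then shows only slight shrinkage. If incomplete forms cannot be submitted, the effect is nil.
- Dividing by answered items assumes that skipped items resemble answered ones. Requiring complete scales is a defensible alternative, but it would abandon the SAP's own 25% rule and discard data.
- The endpoint is exploratory, reported descriptively and outside the testing hierarchy in SAP 4.6.

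**Conclusion.** The point holds as a scoring defect in SAP 4.5.2. The retention rule and the fixed denominators, applied together as written, understate any retained incomplete scale. For skipped items that would have matched the answered ones, the understatement is 20% for lifestyle or convenience with one gap, and 6.25% to 25% for the overall score with one to four gaps, provided the 25% rule applies to the overall score.

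The documents do not support a claim that the mean DM-SAT change will be biased by a given amount or in a given direction. Under the assumed means, with 10% of participants skipping one of five items, a true +0.200 would be reported as +0.186 (Week 16 only), +0.210 (baseline only) or +0.196 (both visits). The TIR correlations that use lifestyle, convenience or the overall score are exposed too, by an amount that cannot be derived from the documents. No primary or key secondary result depends on these scores. It should be corrected because the error is avoidable at almost no cost.

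**What to change.** In SAP 4.5.2, replace the fixed denominators with one rule for all five scores, naming the overall score explicitly: when 25% or fewer of the items in a scale are missing, score = sum of answered items / (10 × number of answered items); otherwise the scale is missing.

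In the constant-7 example this returns 0.70 however many retained items are skipped. The cost is one sentence in the SAP and one line of derivation code, with no new data. The small downside is the assumption that skipped items resemble answered ones, which should be stated beside the rule.

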4.6 MULTIPLICITY ISSUES

A hierarchical testing procedure will be performed. Key secondary endpoints will be evaluated with a one-sample two-sided t-test ($t = \frac{\bar{x} - \Delta}{\frac{s}{\sqrt{n}}}$) to determine whether there is any change between baseline (run-in) and week 16. The overall type-I error rate will be controlled at the two-sided 0.05 level using a sequential testing procedure. For any secondary endpoints to be eligible for being declared significant, the primary endpoint must be significant at 0.05 significance level. The secondary endpoints will be tested following the hierarchical testing procedure with a pre-specified order, that is, inferential conclusions about successive secondary endpoints require statistical significance at 0.05 significance level of the previous one. The following key secondary endpoints will be tested in the following order:

- Change (%) from baseline to week 16 in coefficient of variation
- Change (mg/dL) from baseline to week 16 in mean daily blood glucose
- Change (mg/dL) from baseline to week 16 in the maximum PPG exposure in the 4 hours after the breakfast meal (MMTT)
- Change (%) from baseline to week 16 in TAR (>180 mg/dL)

If at any step the null statistical hypothesis is not rejected, the endpoints listed after that step will be reported at nominal level, otherwise will be technically eligible for being declared significant.

A summary table will present the mean, 95% CI, p-value, and the statistical significance for the primary endpoint and the key secondary endpoints.

4.7 SAFETY ANALYSES

All safety analyses will be performed on the safety set as defined in [Section 3](#), unless otherwise specified, using the following common rules:

- The analysis of the safety variables will be analyzed descriptively, and no testing is planned. Planned analysis is described in further detail below.

The safety endpoints include number of participants with adverse events (AE), serious adverse events (SAEs), adverse events of special interest (AESIs), overall hypoglycemia, and confirmed hypoglycemia.

Hypoglycemia rates during 16 weeks of treatment, including the percentage of participants with at least 1 hypoglycemia event and number of events per participant year, will be analyzed descriptively in a table. Further explanation is described below in hypoglycemia section.

4.7.1 Extent of exposure

The extent of study treatment (specifically, insulin glargine) exposure and adherence will be assessed based on the safety set, presented by the following parameters:

- Duration of treatment;
- Mean planned dose, i.e., doses documented in CRF Exposure page;
- Mean actual dose, i.e., doses recorded in diary by participants;
- Minimum planned dose;
- Maximum planned dose;
- Last planned dose, i.e., the planned dose documented in CRF at the last visit;
- Number of participants whose planned dose reached at least 60 units/mL.

The lixisenatide dose will not be presented; instead, a footnote that states the ratio of insulin glargine (in unit/mL) to lixisenatide (in µg/mL) equals 3:1 will be included wherever applicable.

Duration of IMP exposure

The duration of IMP exposure will be calculated as date of the last IMP injection – date of the first IMP injection + 1. If the date of the last dose of IMP (in the eCRFs) is missing, the duration of IMP will be left as missing.

Duration of IMP exposure will be summarized quantitatively using descriptive statistics and categorically as below:

- ≤ 8 weeks
- > 8 weeks to ≤ 16 weeks
- >16 weeks

Additionally, the cumulative duration of treatment exposure will be provided, defined as the sum of days of the duration of treatment exposure for all participants divided by 365.25, and will be expressed in participant years.

A summary of the number and percentage of subjects with any visit impacted by the COVID-19 pandemic may be produced, if applicable. The summary will include the number of visits and assessments impacted, as well as the reasons for the impacted visits/assessments.

Treatment adherence

A given administration will be considered nonadherent if the participant did not take the planned dose of treatment as required by the protocol. No imputation will be made for participants with missing or incomplete data.

The adherence rate for a participant will be defined as the total number of days with a Soliqua 100/33 injection divided by planned number of days with Soliqua 100/33 injection multiplied by 100.

Treatment adherence will be summarized using the mean, SD, median, minimum, maximum and range, using the safety set. In addition, the percentage of participants who have <60%, ≥60% to <80%, ≥80% to ≤100%, and >100% adherence will be summarized.

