13.3 Appendix: Participant eDiary Information

Participants will be provided with an eDiary to use during the study. Participants will be instructed on how to complete the eDiary.

eDiary completion will occur from the screening period (Visit 1) through the follow-up period (Visit 8). The participant is expected to return for site visits with the eDiary completed. The eDiary will be reviewed by the study site staff by viewing the data transmitted from eDiaries into the database.

The following information is to be recorded in the eDiary:

- Each dose taken (date/time and actual dose). The participant will document any temporary treatment discontinuations.
- Fasting SMPG values before breakfast at least 3 to 4 times per week throughout the study period (to inform each dose adjustment).
- Symptoms of hypoglycemia: Participants will be trained on the hypoglycemia eDiary completion requirements and the need to contact the investigator as soon as possible in case of a significant hypoglycemia occurrence, so that appropriate actions can be taken (eg, intolerance to the study drug injection).
- If assistance to resolve the hypoglycemia event was required out of necessity or convenience.

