- Number and percentage of participants with at least 1 hypoglycemia event and number of hypoglycemic events, by ADA classification levels

- Number and percentage of participants with at least 1 hypoglycemia event and number of hypoglycemic events, by observation periods
- Documented Hypoglycemia
 - Documented symptomatic hypoglycemia
 - Documented serious symptomatic hypoglycemia
 - Documented non-serious symptomatic hypoglycemia
 - Asymptomatic Hypoglycemia
- Symptomatic Hypoglycemia
- Pseudohypoglycemia
- Nocturnal Hypoglycemia Defined by Time of the Day, overall and by ADA levels
- Nocturnal Hypoglycemia Defined by Sleep Status, overall and by ADA levels
- Daytime Hypoglycemia Defined by Time of the Day: overall and by ADA levels
- Daytime Hypoglycemia Defined by Awake Status, overall and by ADA levels

In addition, rate of on-treatment symptomatic hypoglycemic events (Overall, and by time of day per ADA levels) will be summarized in a table whereas

Hypoglycemic events rate per participant year = Number with hypoglycemic events/Total Person Years

If there are multiple events from an individual participant, all events will be counted.

where Total PY is calculated as below:

Observation period	Total Person Years	Time to event (days)	Censoring time (days)
On-treatment	(cumulative total time to event date for participants with event + cumulative total of censoring time for participants without event)	date of event -first dose date +1	(last dose date+1) -first dose date +1

Participants with symptomatic hypoglycemia events, and participants with severe hypoglycemia events will be displayed in listings. A figure will be provided showing the time to the first severe or documented ADA Level 3 symptomatic hypoglycemia during on-treatment period.

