4.7.4.2 Product complaints

Any defect in the IMP device must be reported as soon as possible by the investigator to the monitoring team, who will complete a product complaint form within the required timelines.

Appropriate information (eg, samples, labels, or documents like pictures or photocopies) related to product identification and to the potential deficiencies may need to be gathered. The investigator will assess whether the quality issue must be reported in association with an AE or SAE.

All product complaint summaries during the on-treatment period (see [Section 4.1](#)) will be generated using the safety set and will include the number (%) of participants experiencing at least one event, the number of events, and the event rate per participant-year.

The event rate per participant-year will be defined as the number of events divided by the cumulative duration of all participants' exposure expressed in years.

The overview of product complaints with the details below will be generated:

- Any product complaint
- Any product complaint related to AEs

In addition, the analysis below will be conducted.

- Any product complaint categorized by type of complaint
- AE(s) leading to product complaints by primary SOC and PT

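### When the eCRF last-dose date is missing, SAP 4.7.1 discards the participant's whole treatment duration, although the eDiary is meant to date each dose and could supply a fallback

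*SAP*

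**What the plan says.** SAP 4.7.1 defines duration of exposure as last injection date minus first injection date plus 1, and then adds: "If the date of the last dose of IMP (in the eCRFs) is missing, the duration of IMP will be left as missing". Cumulative exposure is "the sum of days of the duration of treatment exposure for all participants divided by 365.25". The product-complaint rate in SAP 4.7.4.2 is the "number of events divided by the cumulative duration of all participants' exposure expressed in years".

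A second dated record of dosing is planned. Protocol 13.3 lists "Each dose taken (date/time and actual dose" among the eDiary entries and has site staff review the diary by "viewing the data transmitted from eDiaries into the database". SAP 4.7.1 itself uses that source in another row of the exposure summary: "Mean actual dose, i.e., doses recorded in diary by participants".

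Two other places need a last-dose date and do not say what happens without one. In SAP 4.7.3, the person-time of a participant with no hypoglycemia event is ("last dose date+1) -first dose date +1". The treatment-emergent windows end a fixed number of days after the last administration: 3 days for adverse events (SAP 4.7.2) and 1 day for hypoglycemia (SAP 4.7.3). SAP 5.4.4 covers missing onset dates and a missing first dose, but not a missing last dose.

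**The concern.** The rule turns one absent date into the loss of all of a participant's time on drug, even where the diary shows dated doses over most of that time. The same participant could then contribute to mean actual dose and be absent from duration.

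Three outputs follow directly: the duration summary and its categories, the cumulative participant-years, and the complaint rate. For the complaint rate the error has a direction. The time leaves the denominator and nothing removes the complaints, so the rate can only rise.

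A completer is dosed on site at Visit 7, so the last-dose date should be known. A participant lost to follow-up cannot be asked for it. If missing dates cluster in that group, the discarded durations would mostly be short ones, mean duration would be too high and the lowest duration category too small. That clustering is plausible, but the documents do not establish it.

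**Working it through.** The plan states no expected exposure, so there is no figure of its own to reproduce. The check asks how much participant-time the rule could remove.

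**Inputs from the documents.** 100 enrolled and about 15% discontinuing before Week 16 (SAP 2), hence 85 completers and 15 drop-outs. A completer runs from Day 0 to Day 112 (Protocol 13.1), which is 113 days by the SAP formula.

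**Assumptions.** Mean days on drug among drop-outs, d, from 14 to 84. Number of drop-outs without an eCRF last-dose date, k, from 1 to 15.

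**Formulas.** Total days T = 85 × 113 + 15d = 9,605 + 15d. Share lost = kd / T. Inflation of the complaint rate = T / (T − kd). Mean duration shown = (T − kd) / (100 − k).

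| d | T in days (participant-years) | lost, k = 1 | lost, k = 5 | lost, k = 15 |
|---|---|---|---|---|
| 14 | 9,815 (26.87) | 0.14% | 0.71% | 2.14% |
| 28 | 10,025 (27.45) | 0.28% | 1.40% | 4.19% |
| 56 | 10,445 (28.60) | 0.54% | 2.68% | 8.04% |
| 84 | 10,865 (29.75) | 0.77% | 3.87% | 11.60% |

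**Complaint rate.** With k = 5 it is multiplied by 1.007 at d = 14, 1.028 at d = 56 and 1.040 at d = 84.

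**Mean duration.** At d = 56 it is 10,445 / 100 = 104.5 days with everyone included, and (10,445 − 280) / 95 = 107.0 days with five missing.

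**Lowest duration category.** If all 15 drop-outs stopped at exactly 56 days, the row for 8 weeks or less would hold 15 participants, and 10 with five dates missing. At d = 84 nobody is in that row and nothing changes. So the row can move more in relative terms than the person-time does, but only when the affected participants stopped by Day 56. Short exposures also remove less person-time, so the two effects are not at their largest together.

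**Hypoglycemia rate.** This has its own formula in SAP 4.7.3. A participant with an event contributes time from first dose to the event, which needs no last-dose date. Only event-free participants need it. If a missing date meant no censoring time, then at d = 56 with all 15 dates missing the rate would be multiplied by 1.00 if all 15 had an event, 1.042 if half were event-free and 1.087 if all were event-free. These factors count full time on drug for everyone else. Person-time stopping at the event makes the real denominator smaller and the factor somewhat larger for the same lost time.

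**The case against.** The best reply is that few dates will be missing. Permanent discontinuations must be recorded in the eCRF (Protocol 4.4.1.1), all eCRF fields are to be completed (Protocol 8.8.1), dates of administration are source data (Protocol 13.8), and the monitor checks the administration page against returned drug and the treatment log (Protocol 5.10). The rule covers only what remains after that. This stands, and it is why 1 to 5 missing is a more sensible range than 15. It does not say what to do with the remainder.

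A second reply is that leaving the value missing is open and consistent. SAP 5.4.4 does the same when the first-dose date is missing, and SAP 4.1 reports the number of observations, so a shortfall in the duration summary would show. That is fair for the duration rows. The cumulative total and the complaint rate are single figures, and neither section asks how many participants stand behind them.

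A third is that the diary is completed by participants, and someone who drifts out of the study may stop entering doses before stopping the drug. This also stands: the last entry is a lower bound, not the true date.

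A reader might infer more than the documents support:
- *Early drop-outs as a group vanish from the exposure table.* They do not. Only those without an eCRF last-dose date are affected, and only in duration-based rows. The planned-dose and actual-dose rows need no last-dose date.
- *The quoted sentence governs the hypoglycemia rate.* It does not. That rate does not use the duration variable, and participants with events keep their time. The gap there is a separate silence in SAP 4.7.3.
- *The missing dates are known to be informative.* The documents report neither how many will be missing nor in whom.

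**Conclusion.** The point holds in a limited form. SAP 4.7.1 discards all of a participant's exposure time for want of one eCRF date when a second dated source is planned, reaches the database and is already used in that section. The direct effect falls on the duration summary and categories, cumulative participant-years and the complaint rate. The undefined hypoglycemia censoring time and treatment-emergent windows are a related but separate gap.

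The size is probably small: about 0.1% to 3.9% of participant-years if 1 to 5 of 15 drop-outs lack the date. This rests on assumed counts and assumed days on drug. The 11.6% figure requires every drop-out to lack the date at 84 days each, and nothing in the documents suggests that. Safety is analysed descriptively without testing (SAP 4.7), and the primary and key secondary analyses do not use this variable. It is an optional improvement, worth making because it is cheap and best settled before database lock.

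**What to change.** In SAP 4.7.1, replace the sentence with a rule: if the eCRF last-dose date is missing, take the date of the last dose recorded in the eDiary and treat it as a lower bound. If the diary has no dated dose either, leave duration missing. Use the same derived date for the product-complaint denominator (4.7.4.2), the censoring time in 4.7.3 and the ends of the treatment-emergent windows. Report how many participants had the date filled from the diary and how many remain missing.

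The cost is one or two sentences and a short derivation. The downside is that the last diary entry may precede the true last dose, so exposure may be somewhat understated for those participants. An early date would also close the adverse-event window early, so events in these participants that fall after the derived window should be listed, to show any moved to the post-treatment period. If no eCRF date is missing, no result changes.
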